5-24-2021

Pharmacologically-based Strategies for Opioid Substitution Therapy During Pregnancy

PRO18070495 / STUDY19100128

NCT03831113

Protocol version 1.8

The Eunice Kennedy Shriver National Institute of Child Health and Human Development (NICHD)

Principal Investigator:

[name]
Magee-Womens Hospital
[name]
[name]

Specific Aim 4

Specific Aim 4 compares dose reduction strategies for Suboxone or Subutex in pregnancy that are based on the pharmacodynamic and pharmacokinetic characteristics of BUP.

a) Primary Research Questions

1. Is adherence during dose reduction influenced by the magnitude or frequency of a given dose reduction?
2. Is adherence during dose reduction influenced by dosing frequency?
3. Does mu receptor sensitivity change during dose reduction?

b) Eligibility Criteria

Inclusion Criteria – must meet all of the following:

1. On a stable BID, TID or QID dosing regimen of BUP for at least 2 weeks as part of an established medication- assisted treatment (MAT) program.
2. Willingness to undergo supervised dose reduction
3. Subjects on BID, TID or QID dosing, willing to be assigned to the Magnitude, Frequency, or Dosing group, depending on their current dosing
4. Single gestation between 14-30 weeks at the initiation of dose reduction
5. On a BUP dose between 6- 24 mg daily (lower doses will not provide sufficient data points)
6. Willingness to have urine samples tested for drugs of abuse and blood samples tested for BUP+M concentrations during the Medical Supervised Withdrawal (MSW) clinic appointments
7. Willingness to attend weekly or biweekly MSW clinic appointments and to have daily contact via text messaging to complete daily logs of sleep quality, withdrawal symptoms and symptoms of craving. Subjects may consent to receiving daily text messages with a link to a REDCap where they can complete the daily questionnaires electronically. Alternatively, they may complete hard copies of the questionnaires and return them during their weekly clinic visits.
8. Willingness to attend psychosocial support meetings, as needed.

Exclusion criteria – cannot meet any of the following:

1. Current use of cocaine, heroin, benzodiazepines, barbiturates, phencyclidine (PCP), or opioids other than BUP
2. Currently taking more than two mental health medications

3. Active moderately severe depression (PHQ-9 score ≥ 15 or suicidal ideation)
4. Current incarceration

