In all 3 groups, daily adherence, cravings and sleep measures will be compared within and across groups. During the Pre-Study Screening, we will explain the study to the subject and ask that she completes an Intake Questionnaire to better understand any previous experiences she may have had with opioid treatment or detox programs. We will also perform urine and blood testing to assure all entry criteria are fulfilled. Once consent is obtained, we will initiate a Suboxone or Subutex dose reduction schedule similar to the one shown in Table 1. To ascertain the impact of a dose change, all subjects will complete 4 daily VAS questionnaires similar to those used by Dunn et al. ⁴⁶ to assess withdrawal, cravings, sleep duration and sleep quality. The scales will range from a score of 0-10 for each question. Subjects that wish to be contacted via text will be sent a daily text with a link to the REDCap website where they can complete the VAS

questionnaire electronically throughout the dose reduction process. Subjects that are unable to receive daily text messages will be provided hard copies of the VAS questionnaire and instructed to return the completed forms to research staff at their next appointment. Clinic visits will occur weekly or biweekly at which time we will monitor plasma BUP+M, neurotransmitter and cotinine concentrations and perform a comprehensive urinary toxicology test. Additionally, at each clinic visit we will administer the Weekly Follow-up and Weekly Smoking and Alcohol Use questionnaires. We will also collect any completed VAS forms, if applicable, and perform COWS and Subjective Opioid Withdrawal Scale (SOWS) scores to assess current clinical and subjective symptoms of withdrawal and satiety. All subjects will receive psychosocial support, as needed. The timing of the subject's scheduled visits will be determined by their healthcare provider.

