Since our focus is to assess whether the magnitude of the dose change, frequency of dose change and dosing frequency impact adherence during reduction, this pharmacodynamic study will be completed when the subjects are off BUP entirely or on the lowest tolerable dose. However, we will continue to see the subjects weekly or biweekly, monitor their adherence and continue to provide counseling sessions, as needed, until the 6-week postpartum visit. We will also evaluate peripheral blood mononuclear cells (PBMCs) as a surrogate marker of metabolic enzymes and transporters. The expression of drug metabolizing enzymes and transporters in the PBMCs will be correlated with the plasma concentrations of BUP and its major metabolites. Two maternal blood samples will be drawn for PBMC analysis; one during pregnancy and one in postpartum. The first sample will be drawn during the Pre-Study Screening; however, if this is not possible, it may be drawn at any time during pregnancy. The second sample will be drawn at 4-6 weeks postpartum, but as close as possible to the 6-week postpartum visit.

For subjects not enrolled in specific aim 3a or 3b, we will collect a cord blood sample at the time of delivery as well as maternal and newborn hair within 3 days of delivery, when possible. An additional cord blood sample (10 mL) will be drawn for genetic studies related to metabolizing enzymes, if the mother consents. The minimal amount of hair needed is 20 mg but we will ask for 100 mg which is still a very small amount. Hair will be removed from the mothers and baby's head (if consent is granted). Mother will decide where the hair will

be removed from her and her baby. The collection of these samples will be described in full detail during the consent process.

Note: Subjects that consent to participate in specific aims 3 (Parts 1 or 2) will already have the cord blood and hair samples collected as part of that specific aim. The collection of these biological samples only applies to those subjects not already enrolled in specific aim 3.

Table 1.

Dose Reduction Schedules if Start Dose is 16 mg Daily			
Group	Frequency	Magnitude	Dosing
Strategy	Reduce dose by 2 mg weekly then biweekly, repeat till dose=0 or at the lowest possible dose	Reduce dose by 1 and then 2 mg weekly, repeat above till dose=0 or at the lowest possible dose	May elect either the Frequency or Magnitude dose reduction schedule.
Dosing Frequency	QID or TID	QID or TID	BID
Dose			

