Week 1	16	16	Refer to the appropriate dose schedule in the Frequency or Magnitude columns
Week 2	14	15	
Week 3	14	13	
Week 4	12	12	
Week 5	10	10	
Week 6	10	9	
Week 7	8	7	
Week 8	6	6	
Week 9	6	4	
Week 10	4	3	
Week 11	2	1	
Week 12	2	0	
Week 13	0	0	

e) Statistics

The outcome(s) of interest are the pharmacodynamic endpoints that reflect the acclimatization of the mu receptors and opioid-affected brain functions. Each subject in a group will undergo alternating treatments to minimize any between subject differences that would impact the response to the decrease in dose. In this study, we will rely on scores from the self-administered VAS questionnaires. We will determine both an average and highest value for each of the VAS questionnaires weekly. The average values over the 7 days of

that given dose from the VAS questionnaires will be combined to create a single score for each week. A similar approach will be taken for the highest rather than average values. Based on the study of Dunn et al ^{46,47}, the mean value for the withdrawal VAS questionnaire (scale 1-10) in non-pregnant subjects was 30 with a standard deviation of ~25. These values are estimates since graphs were provided but not tabular data. A difference of 25% in the VAS combined scores between any of the comparisons would seem clinically meaningful. Thus, a sample size of 10 in each group is sufficient to detect a difference in VAS scores between any of the comparison groups. The comparisons in the Frequency group will be VAS scores between the 1 vs 2 week reductions. The comparisons in the Magnitude group would be VAS scores between the 1 and 2 mg reductions. The comparison in the Dose group will be a comparison of the VAS scores during the 1 mg and 2 mg reductions. Also, VAS scores in the Dose group will be compared to the VAS scores in the Magnitude group both at the 1 and 2 mg reductions. The change in mu receptor sensitivity will be determined by comparing the BUP+M

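### Primary questions 1 and 2 ask about adherence, but adherence has no definition, designated source or specified analysis, and every group comparison in section e is on VAS symptom scores

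*Combined protocol and SAP*

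**What the plan says.** Section a) Primary Research Questions asks "Is adherence during dose reduction influenced by the magnitude or frequency of a given dose reduction" and "Is adherence during dose reduction influenced by dosing frequency". The third question concerns mu receptor sensitivity. Section d) Study Design restates the focus as whether the "magnitude of the dose change, frequency of dose change and dosing frequency impact adherence during reduction", and says that "daily adherence, cravings and sleep measures will be compared within and across groups".

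The daily instruments named in section d are four VAS questionnaires "to assess withdrawal, cravings, sleep duration and sleep quality". Section e) Statistics opens differently from section a: "The outcome(s) of interest are the pharmacodynamic endpoints that reflect the acclimatization of the mu receptors and opioid-affected brain functions". It continues: "In this study, we will rely on scores from the self-administered VAS questionnaires". It then specifies comparisons of VAS scores only, and bases the sample size on a 25% difference in the combined VAS score.

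Two other places bear on adherence. Section e assigns a score of 100 on the withdrawal and craving items to women found at visits to have used other opioids. Section G. Subject Removal Criteria drops and replaces women in whom such drugs are detected, and withdraws women who fail to return residual drug more than three times.

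**The concern.** Symptom burden and adherence are different outcomes. A woman can report mild symptoms and still leave the schedule, or feel unwell and stay on it. If the only specified analysis is on symptoms, a lower VAS score after 1 mg than after 2 mg reductions supports a statement about tolerability. It does not show that adherence was better, yet that is what questions 1 and 2 ask.

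The events closest to non-adherence are use of other opioids, stopping and failure to return drug. None is analysed in its own right. Some are absorbed into a symptom score and some remove the woman from the data. A taper schedule could therefore look acceptable on VAS among the women who remain, with its failures uncounted.

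**Working it through.** **1. Questions against specified analyses.**

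| Primary question | Outcome asked about | Comparison in section e | Outcome compared |
|---|---|---|---|
| 1, magnitude | adherence | Magnitude group, 1 mg v 2 mg | VAS |
| 1, magnitude, BID women | adherence | Dosing group, 1 mg v 2 mg | VAS |
| 1, frequency | adherence | Frequency group, 1 v 2 weeks | VAS |
| 2, dosing frequency | adherence | Dosing v Magnitude group, at 1 mg and at 2 mg | VAS |
| 3, mu receptor sensitivity | sensitivity | weekly BUP+M against craving and withdrawal scores | VAS with BUP+M |

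None of the four group comparisons is on adherence. Two of the three primary questions are affected; question 3 has a matching analysis.

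**2. The sample size.** The table gives 25, 15, 10 and 7 for reductions of 15, 20, 25 and 30% in a summed score of 120. The differences are 0.15 × 120 = 18, then 24, 30 and 36 points. The plan states an SD of about 25 for the withdrawal item, but no alpha, sidedness, power or test. Assuming a two-sample t-test, one-sided 5%, 80% power and SD 25 for the summed score, the results are 25, 15, 10 and 7, an exact match. The normal approximation for the third row is n = 2 × 25² × (1.645 + 0.842)² / 30² = 8.6, rounded up to 9; the t-test gives 10. Some paired set-ups come within 2 women of the stated figures, so the design behind the table is not certain. In every case the inputs are VAS values only.

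**3. The announced adherence comparison.** Section d promises to compare daily adherence. The four daily items are withdrawal, cravings, sleep duration and sleep quality, and the daily logs in the inclusion criteria cover sleep quality, withdrawal and craving. No daily item is identified as measuring adherence.

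**4. Where non-adherence goes.** Under section e, other-opioid use raises two of the four VAS items to 100 and then cannot be told apart from symptom burden. Under section G, the same woman is dropped and replaced. If she is replaced and her data are set aside, the failure is lost. If failures cluster after one type of reduction, the contrast among those who remain understates the difference.

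**5. What an adherence analysis could carry.** The Magnitude column of Table 1 runs 16, 15, 13, 12, 10, 9, 7, 6, 4, 3, 1, 0. That is six 1 mg and five 2 mg reductions, so at most 11 steps per woman at that starting dose. The Frequency column holds 14, 10, 6 and 2 mg for two weeks each (4 × 2 = 8 weeks) and 12, 8 and 4 mg for one week each (3 weeks). With a constant weekly event risk p, a one-week interval fails with probability p and a two-week interval with 1 − (1 − p)² = 2p − p², nearly double when p is small. Raw proportions of failed steps would therefore count against the longer interval by construction.

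The documents give no adherence rate, so power can only be illustrated. The figures below are for comparing proportions between two groups of 10, two-sided 5%, normal approximation with pooled variance under the null. All proportions are assumed.

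| Assumed adherent proportions | Power at 10 per group | Per group for 80% power |
|---|---|---|
| 50% v 75% | 20% | 58 |
| 70% v 90% | 19% | 62 |
| 60% v 90% | 33% | 32 |
| 50% v 90% | 50% | 20 |

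Within women, a two-sided signed-rank test with five non-zero differences, all in one direction, gives p = 2 × (1/2)⁵ = 0.0625; with six it gives 0.031. At least six of ten women must therefore differ between step types before 5% can be reached.

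**The case against.** The strongest reply is that much of this is wording. Section d describes the group comparisons as comparisons of tolerance, which symptom scores can reasonably capture, and says that VAS scores will document intolerance in women who return to an earlier dose. On that reading the analysis is right and the questions are loosely phrased. This stands as far as it goes, and it is why rewording is a sufficient fix. But nowhere are tolerance and adherence equated, and section d restates the focus as adherence.

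Three stronger readings are tempting and are not supported.

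- A reader might infer that the trial plans nothing on adherence. Section d announces a comparison and says adherence will be monitored. Plasma BUP+M, urine toxicology and residual-drug return are all available, and the Weekly Follow-up questionnaire, whose content is not shown, may ask about it. What is missing is a definition, a designated source and an analysis.
- A reader might infer that non-adherence enters no comparison at all. Other-opioid use does enter, through the score of 100, though only as a symptom value and in conflict with section G.
- A reader might multiply 11 steps by 10 women and say that 110 adherence outcomes go unused. That is a ceiling: all ten would have to start at 16 mg and complete the taper. Eligible doses run from 6 to 24 mg, section d expects some intolerance, and weekly VAS data from these steps are analysed.

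A simple step-level endpoint also has faults of its own. Section d permits a return to the last tolerated dose, so counting that as non-adherence would penalise women who follow the protocol. Visits may be biweekly, so one urine result can span two weekly steps.

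**Conclusion.** The point holds as a mismatch between question and endpoint. Questions 1 and 2 and the stated focus concern adherence; all four group comparisons in section e, the meaningful difference and the sample size concern VAS symptom scores. Following the plan as written supports a conclusion about symptom tolerance. The documents do not support saying that adherence goes unmeasured or that the trial could not address it.

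The conclusion on endpoints rests on the text and needs no statistical assumption. The sample-size match rests on an assumed test, alpha, power and SD for the sum, and the power figures on assumed proportions. The size of any bias from replacing women cannot be computed, because the documents give no expected rate of removal.

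**What to change.** Choose one of two routes.

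(a) Reword questions 1 and 2, and the restated focus in section d, to ask about symptom tolerance measured by VAS. Remove or define the announced comparison of daily adherence, and state that no adherence conclusion will be drawn from VAS. This changes text only.

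(b) Keep the questions and add an adherence analysis to section e:

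- Name the sources: the dose in force each week, urine toxicology, plasma BUP+M and residual-drug return. The documents name no dose log; I assume the weekly dose is recorded, since section e averages VAS over the days on a given dose.
- Report separately protocol-permitted returns to an earlier dose, other-opioid use, and stopping.
- Keep the data of removed women up to and including the step at which they failed. This is a rule for the analysis set, not for who should be removed.
- Express events per week at risk, so that one- and two-week intervals are comparable, and state how a urine result spanning two steps is assigned.
- Give within-woman contrasts by step type, and BID against TID/QID, as estimates with intervals, labelled descriptive.

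Under either route, reconcile the score of 100 in section e with the drop-and-replace rule in section G, and state what happens to the data of replaced women.

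Route (b) costs one further analysis of data already planned. Its downside is imprecision with 10 women per group, which the plan should state.

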- Subjects in the BID group will be assigned to the Dosing group. The Dosing group may follow the Magnitude (alternating 1 mg and 2 mg dose reductions weekly) or Frequency (2 mg dose reductions on alternating intervals of 1 and 2 weeks) dose reduction schedules.

In all groups, the alternating approach will continue until the subject is Suboxone or Subutex free or at the lowest dose tolerable. We appreciate that some subjects may not tolerate the recommended dose reduction especially at the lower doses. Subjects that experience withdrawal symptoms may be treated with ancillary medications such as Benadryl or clonidine. To minimize any risk of relapse, subjects who are intolerant to a given reduction will be allowed to go back to the last tolerated dose taken prior to the reduction. Visual Analog Scale (VAS) scoring will document their intolerance and this, combined with pharmacological data from the subject, will inform our development of an optimized pharmacological approach to dose reductions. After the subject has been on the higher dose for one week we will re-initiate the dose reduction strategy to which she was assigned. We will repeat this process one more time and if she remains intolerant to further dose reductions, we will not attempt further reductions but rather will maintain her on her current dose. If the subjects desires additional attempts at dose reduction, we will accommodate her request. At this time, she may elect to re-initiate the original dose reduction strategy or select an alternative reduction strategy. For all subjects, we will continue the surveillance approach we have in place throughout the pregnancy, delivery, and into the postpartum period.

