concentration each week to the subjects VAS scores on craving and withdrawal symptoms. In women who supplement their weekly BUP regimen with other opioids detected at the weekly clinic visits their VAS questionnaires on withdrawal and craving will be scored as 100. Assay Methods: BUP+M will be assayed using UPLC-MS-MS. We have developed and validated this assay and with the new TQS system the LOQ is 15 ng/ml in plasma. BUP in hair and other tissues will be measured by modification of this method and incorporating elements of methods reported in the literature ^{30,31,33}. Cotinine will be measured by minor modification of the published method ⁵⁵.

Anticipated sum of mean VAS scores	Percent Reduction in VAS scores	Sample Size
120	0.15	25
120	0.20	15
120	0.25	10
120	0.30	7

D. Study Procedures

D.1 Screening for Eligibility

The inclusion/exclusion criteria will be reviewed with the patient's chart. Any woman who appears to be eligible will be informed about the study. If a patient appears to meet the criteria for enrollment and expresses interest in the study, she will be told about the study and asked to sign the informed consent form. She will be asked to sign a medical records

release so that the medical records may be obtained. A copy of the signed consent form will be provided to the patient.

D.1.i. Gestational Age Determination

We will use the criteria recommended by the American Congress of Obstetricians and Gynecologists (ACOG).

D.2 Informed Consent Procedures and Documentation

Written informed consent will be obtained before entry into the trial. Full disclosure of the nature and potential risks of participating in the trial will be made. Women who are not fluent in English will be enrolled by a person fluent in their language and both verbal and written informed consent obtained in that language; if such are not available, they will not be included.

D.3 Specimen Collection

Per standard research procedures for Labor and Delivery samples, Magee Womens Hospital employs staff as part of the Obstetric Specimen Procurement Unit (OSPU), which is responsible for the collection of research study samples on the Labor and Delivery unit. Labor and Delivery samples will only be collected if possible. There is a 3-day window for collection of hair samples. Maternal and infant samples will be collected as shown in Table 2.

D.4 Specimen Analysis and Collection of Negative Control Samples

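### The statement that 10 women per group suffice for any of the VAS comparisons is not supported by the plan's own inputs: the sample-size table uses a four-scale sum of 120 but gives no SD for it

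*Combined protocol and SAP*

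**What the plan says.** Section d) Study Design says that "all subjects will complete 4 daily VAS questionnaires", covering withdrawal, cravings, sleep duration and sleep quality. Section e) Statistics says of the outcome that "we will rely on scores from the self-administered VAS questionnaires", and that the seven-day averages for "that given dose from the VAS questionnaires will be combined to create a single score for each week".

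The one variability input is in section e): "the mean value for the withdrawal VAS questionnaire (scale 1-10) in non-pregnant subjects was 30 with a standard deviation of ~25". The plan adds that these values are estimates read from graphs. It calls a 25% difference in the combined scores meaningful and concludes that "a sample size of 10 in each group is sufficient to detect a difference in VAS scores between any of the comparison groups".

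The table that closes section e) has a column headed "Anticipated sum of mean VAS scores", set to 120 in every row, and gives sample sizes of 25, 15, 10 and 7 for reductions of 15%, 20%, 25% and 30%. Neither text nor table states an SD for the sum, an SD of paired differences, alpha, sidedness, power or the test.

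Most listed comparisons are within women. One is between different women: "VAS scores in the Dose group will be compared to the VAS scores in the Magnitude group", at both the 1 mg and the 2 mg reductions. On which women supply those data, section d) says: "The Dosing group may follow the Magnitude (alternating 1 mg and 2 mg dose reductions weekly) or Frequency".

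**The concern.** The table's mean of 120 looks like four times the single-scale mean of 30. The SD of a four-scale sum does not follow from one scale's SD without the SDs of the other three scales and the correlations between scales, and the plan gives neither. The word sufficient therefore rests on an input that is not there.

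This matters most for Dose versus Magnitude. Dosing frequency is one of the three primary research questions. The question is worded as adherence, but section e) relies on VAS scores and offers no other basis for the sample size. Dose versus Magnitude is the only comparison listed there that sets BID against TID or QID dosing, and pairing cannot reduce its variance. If the claim stands, a null result could be read as showing that dosing frequency makes no difference, when the contrast may have had little power.

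**Working it through.** **Inputs from the documents.** n = 10 per group; target difference 25% of 120 = 30 points; mean 30 and SD about 25 for the withdrawal VAS; four scales.

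**Assumptions, because the plan is silent.** Alpha 5%, one- and two-sided; power 80%; t-tests by the non-central t distribution, with non-centrality (difference/SD) × √(n/2) for two samples and (difference/SD of differences) × √n for pairs.

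**1. Reproducing the table.** The four rows are differences of 18, 24, 30 and 36 points. At SD 25, two-sample, 80% power:

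| Test | 15% | 20% | 25% | 30% |
|---|---|---|---|---|
| Plan | 25 | 15 | 10 | 7 |
| One-sided 5% | 25 | 15 | 10 | 7 |
| Two-sided 5% | 32 | 19 | 12 | 9 |

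The one-sided version matches every row. Other settings also fit exactly, for example two-sided 5% at an SD of 21.9 to 22.0. Exact paired fits, searching alpha 5% or 10% and power 70% to 90%, appear only at one-sided 10%, with an SD of differences from 33.9 to 48.9. That the single-scale SD was carried over is thus the simplest reading, not a stated fact. At SD 25, power with 10 versus 10 for 30 points is 82% to 83% one-sided and 72% two-sided.

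**2. SD needed, one weekly score per woman.** With 10 versus 10, 80% power needs difference/SD of 1.325 (two-sided) or 1.156 (one-sided). The largest tolerable SD of the sum is 30/1.325 = 22.6 or 30/1.156 = 25.9.

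**3. SD if every scale had SD 25.** SD of the sum = 25 × √(4 + 12r), where r is the mean inter-scale correlation. This gives 50 at r = 0 and 100 at r = 1. It equals 25 only at r = −0.25.

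| SD of sum | Power two-sided | Power one-sided | 95% CI half-width |
|---|---|---|---|
| 50 | 25% | 36% | 47 points |
| 100 | 10% | 16% | 94 points |

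Half-width = 2.101 × SD × √(2/10).

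**4. Averaging repeated steps.** Averaging k weeks with week-to-week correlation ICC multiplies the SD by √(ICC + (1 − ICC)/k). Table 1's Magnitude column, from 16 mg, has six 1 mg and five 2 mg steps. Applying the same alternation to the eligible starting doses gives about 2 steps of each size from 6 mg and 8 from 24 mg. The ICC is not stated; 0.1 to 0.7 is assumed.

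| SD of one weekly sum | k = 2, ICC 0.7 | k = 8, ICC 0.1 |
|---|---|---|
| 50 | SD 46.1; 28% two-sided, 40% one-sided | SD 23.0; 79% two-sided, 88% one-sided |
| 100 | SD 92.2; 11% two-sided, 17% one-sided | SD 46.1; 28% two-sided, 40% one-sided |

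The limits in step 2 rise accordingly. With k = 6 and ICC 0.1 the factor is 0.5, so the one-sided limit is 25.9/0.5, about 52.

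**5. Paired contrasts.** Ten pairs have 80% power for 30 points if the SD of the differences is at most 30.1 (two-sided) or 35.2 (one-sided). None is stated.

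**6. Usable numbers.** Table 1's Frequency column contains only 2 mg steps. Each Dosing-group woman who follows it contributes nothing at 1 mg, so contrasts that use 1 mg steps may have fewer than 10 Dosing-group women.

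**7. Scale.** Section d) gives each question a range of 0 to 10, so four questions total at most 40. Section e) gives a 1 to 10 scale with a mean of 30, and scores withdrawal and craving as 100 when other opioids are detected. Rescaling mean and SD together leaves the power figures unchanged, but 120 cannot occur on the range in section d).

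**The case against.** The strongest reply is that low power has not been shown. The table reproduces, and at the only SD in the plan one-sided power exceeds 80%. The figures of 50 to 100 need SD 25 on all four scales and a non-negative mean correlation. The plan does not say whether about 25 is a daily or a weekly SD. If daily, a seven-day mean varies less: with an assumed day-to-day correlation of 0.5 the factor is √(0.5 + 0.5/7) = 0.756, so 50 becomes 37.8. Sleep scales scored in the opposite direction to withdrawal and craving could also shrink the SD of the sum, though a uniform 25% worsening would then cancel (+7.5 + 7.5 − 7.5 − 7.5 = 0). This is also a small study with hedged wording.

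Most of that stands. A reader might infer that the table contains an arithmetic error; it does not, and the gap is an undocumented assumption. A reader might infer that 22.6 or 25.9 is a hard ceiling on the SD; it applies only to one weekly score per woman. A reader might infer that the trial is underpowered and needs more patients; the documents do not support that, because the SDs of three scales, the inter-scale correlations and the week-to-week correlation are all missing. None of this supplies the missing input, and the hedging does not extend to the claim that 10 is sufficient for any comparison.

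**Conclusion.** The concern holds as a failure of support. For Dose versus Magnitude, and for the paired contrasts, the plan does not demonstrate that 10 per group can detect 25%, and it does not provide what would be needed to check. Under the assumed SD of 25 on each scale and non-negative correlations, two-sided power for Dose versus Magnitude runs from about 10% to 25% on single weekly scores. At the favourable end of that range (SD 50), averaging over steps gives roughly 28% to 79%. One-sided, with many averaged steps and a low week-to-week correlation, 80% can be reached. The range is wide because the inputs are absent. The absence of an SD for the sum is visible in section e) and needs no reconstruction; how the table was computed remains an inference. This should be fixed, because the dosing-frequency question has no other sample-size basis.

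**What to change.** - Reconcile the VAS range between section d), the mean of 30 in section e) and the score of 100, and state the scoring direction of the sleep scales.
- Replace the table with one that states the test, alpha, sidedness, power and an SD for the summed weekly score. Because the source gave graphs only, show a sensitivity range over inter-scale and week-to-week correlation rather than a single value.
- Give separate lines for the paired contrasts (with the SD of differences) and for the two-sample contrast, the number of weeks averaged, and the number of Dosing-group women expected to contribute 1 mg steps.
- Replace the blanket sufficiency sentence with the differences that 10 per group can detect.
- Present Dose versus Magnitude as estimation with a 95% confidence interval unless a justified SD supports 25%.

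The cost is a few sentences and one table in section e), some work to justify the range of SDs, and a less favourable stated detectable difference. No extra patients are required.
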